5.9.1	Triptorelin Plasma Concentrations	23
5.9.2	Triptorelin PK Analysis	23
5.10	Anti-drug Antibodies	23
5.11	PD	24
5.11.1	Testosterone Serum Concentrations	24
5.11.2	Testosterone PD Analysis	24
6	DATA HANDLING	24
6.1	Visit Window	24
6.2	Unscheduled Visits, Retest, Withdrawal Visit,	24
7	DERIVED DATA (IF APPLICABLE)	24
8	REFERENCES	24
9	APPENDICES	26
A1.	SAS Code	26
A2.	Partial/Missing Date Convention	27
A3.	Programming Convention for Outputs	29
A4.	Listings Conventions	29
A5.	EudraCT Categories for Age	30
A6.	CTCAE V5.0 Grading for Laboratory Values	31

LIST OF ABBREVIATIONS AND DEFINITION OF TERMS

ABBREVIATION	Wording Definition
AE	Adverse Event
ATC	Anatomic Therapeutic Class
AUC	Area Under the Plasma Concentration Time Curve
BLQ	Below Lower Limit of Quantification
C	Concomitant
CI	Confidence Interval
Cmax	Maximum Observed Concentration
eCRF	Electronic Case Report Form
CS	Clinically Significant
CSR	Clinical Study Report
CTCAE	Common Terminology Criteria for Adverse Events
CV	Coefficient of Variation
gCV	Geometric Coefficient of Variation
DMC	Data Monitoring Committee
ECG	Electrocardiogram
EDC	Electronic Data Capture
EMA	European Medicines Agency
EoS	End of Study
EW	Early Withdrawal
FAS	Full Analysis Set
FDA	Food and Drug Administration
H	High
ICH	International Conference on Harmonisation
IMP	Investigational Medicinal Product
L	Low
LLOQ	Lower Limit of Quantification
MedDRA	Medical Dictionary for Regulatory Activities
NC	Not Calculated
NCS	Not Clinically Significant
NMPA	National Medical Products Administration
NS	No Sample

ABBREVIATION	Wording Definition
NR	Not Reportable
P	Prior
PC	Prior and Concomitant
PD	Pharmacodynamics
PK	Pharmacokinetic
PN	Preferred Name
PPS	Per Protocol Set
PR	Time interval from the start of atrial depolarization to start of ventricular depolarization
PT	Preferred Term
QRS	Time interval for ventricular depolarization
QT	Time interval for ventricular depolarisation and repolarisation
QTc	Corrected QT interval
QTcF	Fridericia corrected QT internal
RR	Time between QRS complexes
SAE	Serious Adverse Event
SAP	Statistical Analysis Plan
SAS	Statistical Analysis System
SD	Standard Deviation
SDTM	Study Data Tabulation Model
SEM	Standard Error Mean
SI	International System of Units
SOC	System Organic Class
SP	Service Provider
t_{castr}	Time to Castration
TEAE	Treatment Emergent Adverse Event
TFLs	Tables, Figures and Listings
t_{max}	Time to Maximum Observed Concentration
WHODRUG	World Health Organisation Drug Dictionary

1 INTRODUCTION

The purpose of this SAP is to outline the planned analyses to be completed to support the completion of the Clinical Study Report (CSR) for protocol D-CN-52014-237. It describes the rules and conventions to be used in the analysis and presentation of data, the data to be summarised and analysed, including specificities of the statistical analyses to be performed.

Exploratory analyses not necessarily identified in this SAP may be performed to support the clinical development program. Any post-hoc, or unplanned, analyses not identified in this SAP performed will be clearly identified in the respective CSR.

The SAP is to be finalised before first participant enters the study. A separate shell will be provided for tables, figures and listings.

Any deviations from the SAP after database lock will be documented in the CSR (section 9.8 “Changes in the conduct of the study or planned analyses” as per International Conference on Harmonisation (ICH) E3).

This analysis plan does not cover pharmacokinetics (PK) and pharmacodynamics (PD) parameters determination and the relationship between triptorelin PK and testosterone PD analysis which will be described in a separate document.

2 PROTOCOL OVERVIEW

2.1 Study Objectives and Hypotheses

The primary objectives of the study are:

- To evaluate the efficacy of triptorelin pamoate 22.5 mg 6-month formulation in achieving castrate levels of testosterone
- To evaluate the efficacy of triptorelin pamoate 22.5 mg 6-month formulation in maintaining the castrate levels of serum testosterone

The secondary objectives are:

- To assess the safety profile including local tolerability of triptorelin pamoate 22.5 mg 6-month formulation
- To demonstrate the effect of triptorelin pamoate 22.5 mg 6-month formulation on prostate-specific antigen (PSA) response
- To assess the PK of triptorelin pamoate 22.5 mg 6-month formulation in a subset of 12 participants with rich PK sampling schedule
- To assess the PD of testosterone in a subset of 12 participants with rich PD sampling
- To assess the PK of triptorelin pamoate 22.5 mg 6-month formulation for all participants
- To assess the PD of testosterone for all participants

The exploratory objective is:

- To evaluate the PK/PD relationship between the PK of triptorelin pamoate 22.5 mg 6-month formulation and testosterone concentration versus time profiles

No statistical hypotheses are planned for this study.

2.2 Overall Study Design and Investigational Plan

This is a prospective, interventional, multicentre, open-label phase IIb, single-arm study with a treatment period of 24 weeks for each participant. A total of 195 Chinese adult participants with locally advanced or metastatic prostate cancer will be enrolled in the study. All enrolled

participants will receive one injection of the 6-month formulation containing 22.5 mg triptorelin pamoate on Day 1.

This study will consist of a 4-week screening period, during which participants with advanced or metastatic prostate cancer will be screened for eligibility. On Day 1, eligible participants will receive a single open-label administration of the study intervention. Following treatment on Day 1, visits will occur on Day 2, Day 3, Day 5, Day 8, Day 15, Day 22 in a subset of 12 participants, and for all participants on Day 29, Day 57, Day 85, Day 113, Day 141 and Day 169.

The maximum duration of the study is approximately 30 months from screening to the last study visit. Participants who complete all scheduled visits will be considered to have completed the study. Participants who complete the study will have final procedures and assessments performed at the final visit (Day 169). Participants who withdraw from the study before the completion of the Day 169 evaluation period will have early discontinuation procedures and assessments performed at their final visit.

2.3 Sample Size Determination and Power

The sample size was estimated based on data from the previous Study DEB-TRI6M-301, 97.5% of participants achieving castration and 93% of participants maintaining castration from Week 8 to Week 24.

Sample size is calculated to fulfil the co-primary efficacy criteria of this study, which is to assess the proportion of participants achieving castrate levels of testosterone on Day 29 and the proportion of participants maintaining the castrate levels of serum testosterone from Week 8 to end of Week 24. A total of 195 participants with advanced prostate cancer will be enrolled to receive the triptorelin pamoate 22.5 mg 6-month formulation.

For an exact binomial test of a proportion with a two-sided nominal significance level of 0.05 and null proportion of 85%, a sample size of 165 participants has an exact power of 88.3% when the true proportion is 93% (of participants maintaining castration from Week 8 to Week 24). This sample size of 165 participants has a power >99.9% when the true proportion is 97.5% (of participants achieving castrate testosterone levels). Exact two-sided 95% confidence interval (CI) for a binomial proportion was computed by Statistical Analysis System (SAS) using the exact binomial distributions.

Assuming the dropout rate will be around 15%, a sample size of 195 participants in total is planned for this study.

2.4 Randomisation and Blinding

This is an open-label study. The study treatment assignment will be known to the participants, investigators, study centres, Sponsor, and any Service Provider (SP) affiliated with the study. Access to the data in the Electronic Data Capture (EDC) system is controlled and limited only to authorised personnel for specified data review.

2.5 Schedule of Assessments

Schedule of assessments is presented in section 1.3 from the protocol.

2.6 Change from Statistical Section of the Protocol

Protocol	SAP
Section 9.4.1.3 Demographic and Other Baseline Characteristics Descriptive summary statistics (n, mean, standard deviation (SD), median, minimum, maximum) or frequency counts of demographic and baseline data (medical history, concomitant disease (predosing AEs and ongoing medical history, prior medications and therapies, etc.) will be presented for the FAS, PP and safety sets.	Section 5.5 Medical history, non-drug therapies, medications and surgical procedures will be present for only Safety Set.

3 PLANNED ANALYSES

3.1 Data Monitoring

No independent Data Monitoring Committee (DMC) will be used in this study.

3.2 Interim Analysis / Primary Analysis

No interim analysis will be performed.

3.3 Final Analysis

Planned analyses will be done when all participants complete study and after database lock.

4 ANALYSIS SETS

Screened Set

The screened set will contain all participants screened (i.e. who signed the informed consent).

Full Analysis Set (FAS)

The FAS will contain all treated participants who complete the study or is a treatment failure. Completing the study is defined as having serum testosterone measurement at baseline, Day 29 and Day 169. Treatment failure is defined as escaping castration (testosterone level ≥ 50 ng/dL or 1.735 nmol/L) at any assessments on and after Day 29 during the study, or premature discontinuation from the intervention period due to drug-related reasons (adverse event or death).

Per Protocol Set (PPS)

The PPS will contain all participants in the FAS who have no impacting major protocol deviations (i.e. that could potentially affect the primary efficacy endpoint outcome for the participant) as described in the protocol deviations document.

Safety Set

The safety set will contain all participants who receive the single dose of study intervention.

Rich PK Analysis Set (for non-compartmental analysis)

The rich PK analysis set will contain all participants in the PK/PD subset who receive one dose of study intervention, have no major protocol deviations affecting the PK variables, and who have a sufficient number of plasma concentrations to estimate the main PK parameters (maximum observed plasma drug concentration (C_{max}), time to maximum observed drug concentration (t_{max}) and area under the plasma concentration time curve (AUC)).

The criteria of major protocol deviations affecting the PK variables will be defined in the protocol deviation document. The process to review major protocol deviations potential impact on PK parameters will be ongoing and the final Rich PK Analysis Set will be determined during data review meeting.

Population PK Analysis Set

The population PK analysis set will contain all participants who received one dose of triptorelin and who have at least one triptorelin plasma concentration and no major protocol deviations affecting PK variables.

Rich PD Analysis Set

The rich PD analysis set will contain all participants in the PK/PD subset who have a sufficient number of PD (testosterone) measurements to estimate the main PD parameters (maximum observed concentration (C_{max}), time to maximum observed concentration (t_{max}) and time to castration (t_{castr})).

The efficacy analysis for the primary and secondary efficacy endpoints will be presented for the FAS and PPS population. The analysis of the safety data will be performed based on the safety set and analysis of PK and PD in the relevant PK/PD analysis set.

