4 STUDY DESIGN

4.1 Overall Design

This is a prospective, interventional, multicentre, open-label phase IIIb, single-arm study with a treatment period of 24 weeks for each participant. A total of 195 Chinese adult participants with locally advanced or metastatic prostate cancer will be enrolled in the study. All enrolled participants will receive one i.m. injection of the 6-month formulation containing 22.5 mg triptorelin pamoate on Day 1.

This study will consist of a 4-week screening period, during which participants with advanced or metastatic prostate cancer will be screened for eligibility. On Day 1, eligible participants will receive a single open-label administration of the study intervention. Following treatment on Day 1, visits will occur on Day 2, Day 3, Day 5, Day 8, Day 15, Day 22 in a subset of 12 participants, and for all participants on Day 29, Day 57, Day 85, Day 113, Day 141 and Day 169. For more details on sampling schedule see the SoA ([Table 1](#) and [Table 2](#)).

The maximum duration of the study is approximately 30 months from screening to the last study visit. Participants who complete all scheduled visits will be considered to have completed the study. Participants who complete the study will have final procedures and assessments performed at the final visit (Day 169). Participants who withdraw from the study before the completion of the Day 169 evaluation period will have early discontinuation procedures and assessments performed at their final visit.

The study design is illustrated in [Figure 1](#).

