5.7.1.3 Statistical/analytical issues

Adjustments for Covariates

This is a single-arm study, and no statistical comparisons will be performed, so covariates adjustment is not required.

Interim Analyses and Data Monitoring

Please refer to section 3.

Multicentre Studies

This is a multicentre study conducted in China.

Multiple Comparisons/Multiplicity

No multiple testing will be performed in this study because this is a single-arm descriptive safety and efficacy study.

Active-Control Studies Intended to Show Equivalence (if applicable)

Not applicable.

5.7.2 *Analysis of Primary Efficacy Endpoint*

5.7.2.1 *Endpoint, Treatment Effect and Estimand Definition*

The co-primary endpoints of efficacy are

- To determine the percentage of participants achieving castrate levels of serum testosterone (<50 ng/dL or 1.735 nmol/L) on Day 29 ± 3 days (Week 4) and
- To determine the percentage of participants maintaining the castrate levels of serum testosterone (<50 ng/dL or 1.735 nmol/L) from Week 8 (Day 57 ± 3 days) to Week 24 (Day 169 ± 3 days).

Percentage of participants achieving castrate levels of serum testosterone on Day 29

The percentage of participants achieving castrate levels of serum testosterone on Day 29 will be obtained as the number of participants achieving castrate levels on Day 29, divided by the number of participants in the FAS. The formula is

$$\text{Percentage} = \frac{\text{Number of participants achieving castrate levels on Day 29}}{\text{Number of participants in the analysis set}} \times 100$$

Percentage of participants maintaining castrate levels from Week 8 to Week 24

Percentage of participants maintaining castrate levels of serum testosterone from Week 8 to Week 24 for the FAS will be calculated as the number of participants achieving castrate levels of serum testosterone at all visits from Week 8 to Week 24, divided by the number of assessable participants in the analysis set. The formula is

$$\text{Percentage} = \frac{\text{Number of participants maintaining castrate levels from Week 8 to Week 24}}{\text{Number of assessable participants in the analysis set}} \times 100$$

To derive the percentage of participants maintaining castration levels of testosterone, missing data between Week 8 and Week 24 will be handled as follows:

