- (a) In participants escaping castration at a certain visit (The escape event is defined as participant with a testosterone level >50 ng/dL), subsequent missing data is irrelevant; that is to say, participant will be treated as failure in that case.
- (b) Participants maintaining castration up to a certain visit with missing data afterwards (drop-out due to non-drug-related reasons) will be excluded from the analysis.
- (c) Participants maintaining castration up to a certain visit with missing data afterwards (drop-out due to drug-related reason) will be treated as having escaped castration (failure). Drug-related reason for drop-out is drug-related adverse event or death.
- (d) Missing data at 1 or more visit(s) between two visits where castration levels are maintained will be handled as missing for that particular visit, and the participant will be considered to have maintained castration if all visits with available results are maintained.

To derive the percentage of participants maintaining castrate levels of testosterone, assessable participants are defined as the number of participants having values at all visits and all participants having missing data according to the criteria a), c) and d) mentioned above. Participants having missing data according to the criteria b) will be excluded from this calculation. Participants who discontinue before Week 8 will also be excluded from this calculation.

Because this is a descriptive post-approval commitment study, and the protocol was approved before National Medical Products Administration (NMPA) implementation of ICH E9 (R1), estimands will not be considered for this study.

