5.7.2.3 Sensitivity Analysis

In addition, to further validate the analysis results of the primary endpoint, below sensitivity analyses will be conducted.

Sensitivity analysis 1: Analysis defined in section [5.7.2.2](#) (primary analyses for co-primary endpoints) will be repeated on the PPS.

Sensitivity analysis 2: Survival analysis to estimate the percentage of participants maintaining castrate levels from Week 8 to Week 24

Percentage of participants with castration levels (<50 ng/dL or 1.735 nmol/L) from Week 8 to Week 24, treated as a time-to-event endpoint, will be analysed by Kaplan-Meier method.

The event is defined as occurring in participants with a testosterone level \geq 50 ng/dL or 1.735 nmol/L between Week 8 and Week 24 (escape event), and it will be presented as number of participants with escape event (event number), percentage of participants with escape event, achievement (<50 ng/dL or 1.735 nmol/L) rate by Week 8, Week 12, Week 16, Week 20, and Week 24 along with 95% CIs (calculated using the Greenwood's formula), minimum, maximum, median and 95% CI for median (calculated using Brookmeyer-Crowley method).

To accommodate drop-out and missing values the following censoring rules will be observed:

Table 5.1 Data Censoring Rules

Subject Discontinued	Week 8 - Week 24/Day of Discontinuation		To Be Handled As
	≥ 1 Missing Testosterone Value	Any Escape*	
Yes	No	No	Censored on day of last measurement
Yes	No	Yes	Event on day of first escape
Yes	Yes	No	Censored on day of last measurement before the first missing
Yes	Yes	Yes	Event on day of first escape
No	No	No	Censored on day of last measurement (date of EOS or Day 169)
No	No	Yes	Event on day of first escape
No	Yes	No	Censored on day of last measurement before the first missing
No	Yes	Yes	Event on day of first escape
No achievement by Week 8			Event on day of Week 8

*The escape (event) is defined as participant with castrate levels of serum testosterone ≥ 50 ng/dL or 1.735 nmol/L.

Below 3 percentages based on different populations are considered for calculation of percentage of participants maintaining castrate levels from Week 8 to Week 24:

Sensitivity analysis 3: All participants treated who complete the study or premature discontinuation from the intervention period due to any reasons will be included.

Sensitivity analysis 4: Participants in the FAS or PPS who do not discontinue from the treatment period prematurely due to drug-related reasons will be included.

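### For the maintenance co-primary, the FAS drops a man with no Day 29 testosterone value if he stays castrate from Week 8 to Week 24 but keeps him if he escapes

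*SAP*

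**What the plan says.** SAP section 4 sets the entry rule: "The FAS will contain all treated participants who complete the study or is a treatment failure". It then defines the first route: "Completing the study is defined as having serum testosterone measurement at baseline, Day 29 and Day 169". The second route, treatment failure, needs either a testosterone level that is not below the 50 ng/dL castration limit or a certain kind of withdrawal, with this wording on timing and cause: "at any assessments on and after Day 29 during the study, or premature discontinuation from the intervention period due to drug-related reasons". Only an adverse event or death counts as such a cause. Protocol 9.3 carries the same rule. The PPS is a subset of the FAS.

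SAP 5.7.2.1 calculates the maintenance rate as the number castrate at all visits from Week 8 to Week 24, "divided by the number of assessable participants in the analysis set". Its missing-data rules (a) to (d) are limited to the same window: "missing data between Week 8 and Week 24 will be handled as follows". Assessability follows from them: "assessable participants are defined as the number of participants having values at all visits", plus those whose gaps fall under rules (a), (c) or (d). Day 29 plays no part.

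SAP 5.7.2.3 describes the population for sensitivity analysis 3 as follows: "All participants treated who complete the study or premature discontinuation from the intervention period due to any reasons will be included". Elsewhere completion is defined by attendance. Protocol 4.1, repeated in SAP 2.2, says: "Participants who complete all scheduled visits will be considered to have completed the study". Protocol 4.4 defines it as finishing all phases, including the last visit.

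**The concern.** The two routes into the FAS ask for different data. A non-failure must have a Day 29 value; a failure need not. For the Day 29 co-primary a Day 29 requirement is at least connected to the endpoint. For the maintenance co-primary it is not, yet it is applied before assessability is considered. Whether a man without a Day 29 value enters the denominator then depends on his result for the very endpoint being estimated.

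At stake is a co-primary estimate and its exact confidence interval. Successes observed in full can be discarded for want of a sample that the endpoint does not use, while failures are never discarded for that reason. The plan is also uneven in what it tolerates: under rule (d) a gap inside the Week 8 to Week 24 window still counts as maintained, but a gap outside it removes the man.

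**Working it through.** **Step 1. Follow one man through the rules.** He is treated, has no Day 29 value, and has values at Weeks 8, 12, 16, 20 and 24.

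| Rule | All five values castrate | One value at or above 50 ng/dL |
|---|---|---|
| Completer under SAP 4 | No (no Day 29 value) | No |
| Treatment failure under SAP 4 | No | Yes |
| In FAS | No | Yes |
| Assessable under SAP 5.7.2.1, FAS aside | Yes, maintained | Yes, failure |
| In the primary maintenance analysis | No | Yes |

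**Step 2. Look for him, castrate throughout, in the sensitivity analyses (SAP 5.7.2.3).**

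- Analysis 1 uses the PPS, which lies inside the FAS: out.
- Analysis 2 (Kaplan-Meier) names no set, so the SAP 5.7.1 default of FAS and PPS applies: out.
- Analysis 4 is restricted to the FAS or PPS: out.
- Analysis 5 is restricted to the FAS or PPS without missing Week 8 to Week 24 data. He meets the data condition but not the set: out.
- Analysis 3 is not restricted to the FAS. Under the SAP 4 definition he neither completes nor discontinues: out. Under Protocol 4.4 he completes: in. Under Protocol 4.1 and SAP 2.2 he is in if he attended Day 29 and only the sample was lost.

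**Step 3. Direction.** With s successes among n assessable men, removing k successes and no failures gives (s − k)/(n − k), which cannot exceed s/n.

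**Step 4. Planning inputs.** SAP 2.3 gives 165 participants, a true maintenance rate of 93%, a null rate of 85%, two-sided 0.05 and 88.3% power. The exact upper-tail rule rejects at 150 or more of 165 (tail probability 0.0173 at 85%). Its power at 93% is 0.8832, so the plan's figure reproduces. The 93% and the 165 are used below.

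**Step 5. Size.** Let p = 0.93 and let m be the share of sustained responders without a Day 29 value. The documents give no value for m, so 2%, 5% and 8% are assumptions. The expected rate is p(1 − m)/(1 − mp), and the expected number removed from 165 is 165 × p × m.

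| m (assumed) | Expected removed | Rate | Shift, points |
|---|---|---|---|
| 2% | 3.1 | 0.9114/0.9814 = 92.87% | −0.13 |
| 5% | 7.7 | 0.8835/0.9535 = 92.66% | −0.34 |
| 8% | 12.3 | 0.8556/0.9256 = 92.44% | −0.56 |

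**Step 6. Effect on the interval.** For illustration, 153/165 is 92.73% with exact 95% limits 87.64% to 96.19%. Removing five such men gives 148/160, which is 92.50% (87.27% to 96.06%). Removing eight gives 145/157, which is 92.36% (87.03% to 95.99%).

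**The case against.** The strongest reply is that the event should be rare and the effect is small. Protocol 8.2 splits each testosterone sample into a primary and a back-up aliquot. Protocol section 8 allows repeat samples for technical problems, Protocol 7.3 asks sites to reschedule missed visits, and SAP 6.2 lets an unscheduled or retest value serve as an endpoint value where appropriate. All of this stands. It lowers the likely m but does not alter the rule, and SAP 6.2 says nothing specific about Day 29. One common set for both co-primaries is also a defensible aim, though the assessable rule already gives them different denominators.

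Several stronger readings are tempting, and the documents do not support them.

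- **No planned analysis includes him.** This is not established. Analysis 3 does so on the visit- or phase-based meaning of completion. The supportable statement is that the SAP does not say which meaning applies.
- **The co-primary as a whole is biased downward.** The direction is certain for this mechanism only. SAP 5.7.2.1 also excludes everyone who discontinues before Week 8, even for drug-related reasons, and that pushes the rate up.
- **The baseline requirement loses men in the same way.** It is nearly empty. Baseline is the last non-missing value before dosing (SAP 5.1.3), and a screening testosterone value is needed for eligibility (Protocol 5.1).
- **The study loses meaningful power.** Exact power moves in a sawtooth with n: at a true 93% it is 86.3% at n = 157, 90.4% at n = 160 and 88.3% at n = 165. A comparison at one chosen n shows nothing. No test is planned (Protocol 9.1, SAP 5.7.1.1), and the 85% null appears only in the sample-size text.

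**Conclusion.** The point holds as a defect of definition. For the maintenance co-primary, FAS entry depends on outcome among men without a Day 29 value: sustained responders are dropped and escapers are kept. Considered alone, this lowers the estimate by about 0.1 to 0.6 points if 2% to 8% of sustained responders lack a Day 29 value, and it lowers the confidence limits slightly. That range rests on the assumed m, the planned 93% rate, and Day 29 values being missing independently of everything else about the responder. The direction needs none of these assumptions. The mechanism works against the product, so it cannot create a false claim of efficacy. Because the effect is small and the correction simple, it should be changed but does not threaten the study's conclusion.

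**What to change.** 1. For the maintenance co-primary, drop the Day 29 requirement. Include treated participants who have all Week 8 to Week 24 values, or who are assessable under SAP 5.7.2.1 rules (a), (c) or (d).
2. Define sensitivity analysis 3 as all treated participants, so that it no longer depends on which meaning of completion is used.
3. Record the departure from Protocol 9.3 in SAP 2.6, since the protocol carries the same FAS text.

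The cost is wording plus that declared change, with no new data. The two co-primaries would have slightly different denominators, which the assessable rule already allows. The change does not touch rule (b), which still removes men who were castrate until a non-drug-related drop-out while keeping those who escaped first. That is a separate choice and should be judged on its own.
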